18. SAP ADDENDUM 3.0

18.1 Forest plots for 24 month rates of Progression-free Survival, Duration of Response and Overall Survival

Forest plots for the 24 month rates of PFS, DoR and OS will be generated for selected non-biomarker subgroups as defined in Section 11.4. The plots will be based on the FAS and will be generated for the IRC response assessment for PFS and DoR. Estimation of the 24 month rates and the pertaining confidence intervals will be based on the Kaplan-Meier method.

19. SAP ADDENDUM 4.0

For the subgroup of centrally confirmed DLBCL patients (see Section 17.8, Non-Hodgkin lymphoma category of *DLBCL*), the following Table will be created:

- Baseline characteristics: tabulation as described in Section 8.5.

The Table will be created based on both the FAS and the SAF.

20. SAP ADDENDUM 5.0

20.1 Exploratory biomarker analyses

Longitudinal analyses will be conducted for: Peripheral numbers of NK cells and B cells (analysed separately):

Tabulations (for NK cells, B cells; based on FAS):

- Summary statistics per visit (a 95% confidence interval for the median will be derived by bootstrapping) by response status (responders vs. non-responders)
- Absolute change from baseline (a 95% confidence interval for the median will be derived by bootstrapping) by response status (responders vs. non-responders)
- Relative change from baseline (a 95% confidence interval for the median will be derived by bootstrapping) by response status (responders vs. non-responders)

Graphical illustrations (for B cells and NK cells; based on FAS):

- Median and its 95% confidence interval (via bootstrapping) for absolute values, absolute change from baseline and relative change per visit across all patients assessed by response status (responders vs. non-responders). The median over time for responders and non-responders will be depicted in parallel in one graph.
- Spaghetti plots displaying the absolute values, absolute change from baseline, and relative change from baseline by visit (i.e., three individual plots for each cell type). The point in time when the PFS event (based on IRC) happened will be indicated in each plot. Each spaghetti plot will only display the subgroup of patients who
 - have a best response PR or CR (at any point in time) and
 - have experienced a PFS event (based on IRC) within 12 months after treatment start with any study drug
- Spaghetti plots displaying the absolute values, absolute change from baseline, and relative change from baseline by visit (i.e., three individual plots for each cell type). Each spaghetti plot will only display the subgroup of patients who
 - have a best response PR or CR (at any point in time) and
 - have NOT experienced a PFS event (based on IRC) within 12 months after treatment start with any study drug

Listing (for B cells and NK cells; based on the SAF)

A Listing will be provided for patients who:

- have a best response PR or CR (at any point in time) and
- have experienced a PFS event (based on IRC) within 12 months after treatment start with any study drug

The Listing will show the following by Visit:

- a) absolute count of B cells and NK cells
- b) absolute change from baseline
- c) percent change from baseline
- d) response category by IRC (if available)

The nominal Visit and the date of the Visit should be indicated for each assessment.

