10.2.4 Censoring rules

12.1.1 Censoring situations

If a patient is alive and progression-free at the date of the analysis (i.e., cut-off date), the patient will be censored, and the reason for censoring will be provided as per Table 13.

The date of last adequate tumor assessment is the date of the last tumor assessment with overall lesion response of CR, PR or SD before an event or a censoring reason occurred. In this case the last tumor evaluation date at that assessment is used. If no post-baseline assessments are available (before an event or a censoring reason occurred) the date of start date of treatment is used.

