**Table 13: Censoring Rules**

Situation	Date of Progression or Censoring	Outcome	Censoring reason
Ongoing and No event until data cut-off	Date of last adequate tumour assessment	Censored	Ongoing
Discontinued the study with no event	Date of last adequate tumour assessment	Censored	Discontinued without event
No baseline tumour assessment	Date of C1D1	Censored	No baseline tumour assessment
Lost to follow-up	Date of last IRC tumour assessment (or C1D1 in case of study discontinuation w/o progression before any post-baseline assessment)	Censored	Lost to follow-up
Patient received non-study anti-DLBCL treatment before disease progression	Date of last adequate tumour assessment before start of non-study cancer treatment	Censored	New anti-cancer therapy started
Clinical Progression*	Date of last adequate tumour assessment	Censored for Analysis based on Investigator assessment only	Clinical Progression not validated by Cheson Criteria
PD by modality not including PET Scan is not confirmed by modality including PET Scan**.	Date of last adequate tumour assessment	Censored for Analysis based on Investigator assessment only	Non-PET PD not confirmed by PET.
Death before any date of PD assessment	Date of death	Progressed	
Death between adequate assessments	Date of death	Progressed	
Death or progression after two or more	Date of last adequate	Censored	Event documented

STATISTICAL ANALYSIS PLAN

 MorphoSys AG
 MOR208C203

Situation	Date of Progression or Censoring	Outcome	Censoring reason
missed visits	tumour assessment		after two or more missing tumor assessments
EOT after two or more missed assessments without disease progression	Date of Last adequate Tumour Assessment	Censored	Adequate assessment no longer available

Abbreviations: EOT = End of Treatment; IRC = Independent Review Committee; PD = progressive disease; CT = Computed tomography; PET = Positron emission tomography. *Progression as per Investigator's assessment and without meeting PD criteria according to Response Criteria for Malignant Lymphoma (Cheson et al., 2007). **The rule only applies in case a PET-including modality is performed after a non-PET including modality.

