13.1.1 Identification of two or more missing tumour assessments

If death or progression happens after two or more missed Tumour Assessments (TA), then the event is censored.

- An event occurring after two or more missing assessments or non-adequate tumour assessments will be censored on the date of last adequate tumour assessment.
- In one of the sensitivity analyses for PFS, an event occurring after two or more missing assessments is back-dated to the date of next scheduled assessment. The date of next scheduled assessment is the date of the last adequate tumour assessment plus the protocol specified time interval for assessments.
- If the patient has an EOT after two missed assessments without an event, then the patient will be censored for PFS at the last assessment and the censoring reason will be 'Adequate assessment no longer available'.
- Table 14 shows the maximum time [days] that can elapse between two response assessments without resulting in censoring.

Table 14: Time windows for missing response assessments

Missed tumor assessments	No tumor assessment between	Censored at
C3D1, C5D1	C1D1, C1D1 + 114 days (4 x 28 + 2)	C1D1
C5D1, C7D1	C3D1, C3D1 + 115 days (4 x	C3D1

STATISTICAL ANALYSIS PLAN

 MorphoSys AG
 MOR208C203

	28 + 1 + 2)	
C7D1, C10D1	C5D1, C5D1 + 144 days (5 x 28 + 2 + 2)	C5D1
C10D1, C12D28	C7D1, C7D1 + 173 days (6 x 28 + 2 + 4 - 1)	C7D1
C12D28, C15D1/C16D1	C10D1, C10D1 + 186 days (6 x 28 + 2 + 2 + 14)	C10D1
C15D1/C16D1, C18D1/C19D1	C12D28, C12D28 + 184 days (6 x 28 + 14 + 2)	C12D28
C18D1/C19D1, C21D1/C22D1	C15D1/C16D1 + 172 days (6 x 28 + 4)	C15D1/C16D1
C21D1/C22D1, C24D1/C25D1	C18D1/C19D1 + 172 days (6 x 28 + 4)	C18D1/C19D1
C24D1/C25D1	C21D1/C22D1 + 451 days (3 x 28 + 2 + 365)	C21D1/C22D1
Tumor assessments in Year 3 and Year 4 after treatment initiation*	C24D1/C25D1 + 730 days (2 x 365)	C24D1/C25D1

*Apply this interval also for assessments after C24D1/C25D1

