20.9 PFS and DoR analyses applying alternative censoring rules

Analyses for the endpoints PFS and DoR will be performed using alternative censoring rules, i.e., three scenarios that led to censoring as per Table 13 will be considered as a PFS event.

Situation	Outcome as per main analysis (see Table 13)	Censoring date as per main analysis (see Table 13)	Outcome as per alternative censoring rules	Date of progression as per alternative censoring rules
Discontinued the	Censored	Date of last	Event	Date of

STATISTICAL ANALYSIS PLAN

 MorphoSys AG
 MOR208C203

Situation	Outcome as per main analysis (see Table 13)	Censoring date as per main analysis (see Table 13)	Outcome as per alternative censoring rules	Date of progression as per alternative censoring rules
study with no event		adequate tumour assessment		discontinuation of the study drug that was discontinued latest*
Patient received non-study anti-DLBCL treatment before disease progression	Censored	Date of last adequate tumour assessment before start of non-study cancer treatment	Event	Date of initiation of non-study anti-DLBCL treatment
Death or progression after two or more missed visits	Censored	Date of last adequate tumour assessment	Event	Date of the first missed tumour assessment (i.e., the planned date of the assessment that was missed)

*Note: in L-MIND, PFS follow-up stops with treatment discontinuation (a post-treatment PFS follow-up is not conducted in L-MIND).

The censoring strategy for the remaining scenarios described in Table 13 will still apply.

The following analyses applying the alternative censoring rules will be conducted:

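### SAP 20.1: the B- and NK-cell plots of responders without a PFS event by 12 months pool patients observed event-free with patients censored earlier

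*SAP*

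**What the plan says.** SAP 20.1 (Addendum 5.0) defines two sets of spaghetti plots for B cells and NK cells, showing absolute values, absolute change and relative change by visit. Both sets are limited to patients who "have a best response PR or CR (at any point in time) and" meet a PFS condition. In the first set the patient had an IRC PFS event within 12 months of treatment start. In the second, patients are those who "have NOT experienced a PFS event (based on IRC) within 12 months after treatment start with any study drug".

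For the first set the SAP adds: "The point in time when the PFS event (based on IRC) happened will be indicated in each plot". It gives no matching instruction for the second set, and no censoring symbol for either.

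The PFS rules are in SAP 10.2.4:

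- The general rule is "If a patient is alive and progression-free at the date of the analysis (i.e., cut-off date), the patient will be censored".
- Table 13 also censors patients who leave the study without an event or are lost to follow-up.
- Table 13 has a row for "Patient received non-study anti-DLBCL treatment before disease progression", censored at the "Date of last adequate tumour assessment before start of non-study cancer treatment".
- The text on missing assessments says: "An event occurring after two or more missing assessments or non-adequate tumour assessments will be censored on the date of last adequate tumour assessment".

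A note under the table in SAP 20.9 states: "PFS follow-up stops with treatment discontinuation (a post-treatment PFS follow-up is not conducted in L-MIND".

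**The concern.** Having no recorded event within 12 months is not the same as being observed event-free for 12 months. The second condition in SAP 20.1 is the plain complement of the first, so it admits every responder whose PFS observation ended early, whatever happened afterwards. A responder who stopped treatment for toxicity at month 4 has no PFS assessment after that, yet meets the condition.

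What is at stake is how the plots can be read. Anyone who compares cell-count courses between the two sets would be looking at one group with known early events and one group of mixed composition: some patients known to be event-free at 12 months, some of unknown status and, through the missed-assessment rule, possibly some who did progress or die before month 12.

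**Working it through.** The plan states no figure for this split, so there is none to reproduce. The check sets the definition against the censoring rules and the scan schedule, then sizes the effect under stated assumptions.

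**1. Can censoring fall before month 12?** SAP 6.6 sets a month at 30.4375 days, so 12 months = 12 × 30.4375 = 365.25 days. Study day = 28 × (cycle − 1) + day. The scans in SAP Table 12 fall at:

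| Scan | Study day | Months |
|---|---|---|
| C3D1 | 57 | 1.87 |
| C5D1 | 113 | 3.71 |
| C7D1 | 169 | 5.55 |
| C10D1 | 253 | 8.31 |
| C12D28 | 336 (332–340 with the ±4-day window) | 11.04 (10.91–11.17) |

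Table 13 mostly censors at the last adequate tumour assessment. A responder censored at any of these scans has less than 12 months of observed PFS and still meets the second condition.

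**2. Can a real event before month 12 be placed in the no-event plots?** SAP Table 14 gives the longest gap allowed before a later event is censored. Adding that gap to the nominal day of the last scan:

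- Last scan C3D1: 57 + 115 = day 172
- Last scan C5D1: 113 + 144 = day 257
- Last scan C7D1: 169 + 173 = day 342

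All three are below 365.25. If the term PFS event in SAP 20.1 follows the main rules of Section 10.2, a responder last scanned at C5D1 who dies on day 300 is censored at day 113 and appears among those without an event.

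**3. Which routes matter?** SAP 5.4.2 places the primary analysis about 12 months after last enrolment, so censoring at data cut-off should be a small source. Stopping treatment, new therapy, loss to follow-up and missed scans are the main ones.

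**4. How large is the pooled share?** Let *e* be the fraction of responders with an event by 12 months and *c* the fraction censored before 12 months. The second group is the fraction 1 − *e* of responders, so the share with unknown status is *c*/(1 − *e*). Neither fraction is in the documents. Assuming *e* = 20–30% and *c* = 10–30%:

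- Low: 0.10/0.80 = 12.5%
- High: 0.30/0.70 = 43%

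For counts, the planning rate in SAP 5.3 gives 0.35 × 80 = 28 responders. At the low end, 28 × 0.10 = 2.8 of 28 × 0.80 = 22.4. At the high end, 28 × 0.30 = 8.4 of 28 × 0.70 = 19.6. That is roughly 3 to 8 patients in a group of 20 to 22.

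**5. What would a strict 12-month rule do?** After C12D28 the next scan is about three months later. A responder who completes 12 cycles event-free and then stops, with no later scan, is censored at about 11.0 months. Requiring a full 365.25 days would remove that patient from the event-free plots, although every scan scheduled before month 12 was done and showed no progression.

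**The case against.** The strongest reply is that the SAP claims little for these plots. They are individual lines under an exploratory heading, with no median, rate, interval or test attached to the 12-month split. The wording is literally true of a censored patient.

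A reader might infer that the second group is presented as durable responders or as progression-free at 12 months, and that the two sets are contrasted side by side. The SAP does not say so. It uses no such label, states no purpose for the split, and specifies a parallel display only for medians of responders and non-responders, which do not use this condition. This part of the reply stands.

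It can also be said that the information is available elsewhere. SAP 20.7.4 lists each patient's PFS time and censoring status, SAP 10.2.5 tabulates censoring reasons, and SAP 10.12.4 defers the comprehensive biomarker work to a separate plan that is not among these documents. A careful reader could identify the early-censored responders, but the plots themselves stay the same.

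Finally, an early stopper may show as a short line. As far as the extracted schedule in Protocol Table 5 can be read (columns may be shifted), flow cytometry ends at about Cycle 8 Day 1, day 197 or 6.5 months. A patient who stopped at month 4 would then have a visibly shorter line. One censored between about 6.5 and 12 months would look like one followed event-free for two years. The reply therefore holds only in part.

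**Conclusion.** The point holds as a minor one. SAP 20.1 states a rule that produces a mixed group. Responders censored before 12 months are pooled with responders observed event-free to 12 months, and nothing specified for the plots tells them apart. This follows from the SAP's own text and needs no assumption, except that placing known events after missed scans in this group requires the PFS definition of Section 10.2 to apply.

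The size is unknown. The 12.5–43% range rests wholly on assumed event and censoring fractions. It is tempting to read it as the share of patients put in the wrong group, but the documents do not support that. Some early-censored responders would have been event-free at 12 months, so the range is a share of unknown status and at most an upper bound on error. Nor do the documents support saying that a result is biased, since no estimate or test uses this split. The primary ORR analysis and the PFS and DoR analyses are unaffected.

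**What to change.** In SAP 20.1, divide responders without an IRC PFS event by 12 months into two groups: those observed event-free to the landmark, and those censored before it. Show the second group in a third panel, or in the same plot with a distinct line style and the censoring time marked. Give the number of patients in each group. State that PFS event and censoring follow Section 10.2, if that is the intention.

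Let an event-free C12D28 assessment, within its ±4-day window, count as completing the landmark. Responders who finish 12 cycles without an event then stay in the event-free group. A responder with an event recorded after that scan but within 12 months remains in the first set of plots.

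The cost is a sentence or two in the SAP and a flag from the existing PFS dataset. The downside is a smaller event-free group and one extra panel or marker.

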20.2 Time since discontinuation of the last treatment

Based on the FAS, the time since discontinuation of the last anti-DLBCL medication before receiving any study drug in L-MIND will be summarized for the following patient subgroups:

- Patients with one prior treatment line
- Patients with two prior treatment lines
- Patients with three or four prior treatment lines

A Listing (based on the SAF) will be provided indicating the time since discontinuation of the last treatment for each patient including the number of previous treatment lines.

20.3 Time since disease progression in the last prior treatment (systemic anti-DLBCL medication)

Based on the FAS, the time since disease progression in the last anti-DLBCL medication before receiving any study drug in L-MIND will be summarized for the following patient subgroups:

- Patients with one prior treatment line
- Patients with two prior treatment lines
- Patients with three or four prior treatment lines

A Listing (based on the SAF) will be provided indicating the time since disease progression in the last treatment for each patient including the number of previous treatment lines.

20.4 Post-L-MIND anti-DLBCL medications

20.4.1 Summaries

Tabulations of anti-neoplastic therapies after discontinuation of MOR00208+LEN

A Table based on the FAS will be provided summarizing anti-neoplastic therapies after discontinuation of all study drugs. The anti-neoplastic therapies will be displayed for the following categories:

- First line after L-MIND
- Second line after L-MIND
- Third line after L-MIND
- Line 4 or higher after L-MIND

Summary statistics for the number of post-L-MIND anti-neoplastic therapies will be provided.

Summary / analysis of OS

A Kaplan-Meier analysis for OS will be conducted focusing only on the period after the end of treatment of both MOR00208 and LEN. The following four patient subgroups will be defined:

Subgroup	Treatment status	PFS Event / Censoring status (based on IRC)	Post-L-MIND anti-DLBCL medication
1	Both MOR00208 and LEN discontinued	PFS Event (deaths not considered)	Experienced (at least one line)
2	Both MOR00208 and LEN discontinued	PFS Event (deaths not considered)	No post-L-MIND anti-DLBCL medication at all
3	Both MOR00208 and LEN discontinued	Censored for PFS follow-up	Experienced (at least one line)
4	Both MOR00208 and LEN discontinued	Censored for PFS follow-up	No post-L-MIND anti-DLBCL medication at all

Baseline for the OS analysis is the earliest point in time when both requirements are met:

- Both study drugs discontinued
- PFS event / censoring happened

A Kaplan-Meier plot will also be generated displaying the four subgroups.

A Table showing the censoring reasons (ongoing at data cut-off, lost to follow-up, ICF withdrawal etc.) for each subgroup will be produced.

A Listing will be provided showing all post-L-MIND anti-DLBCL medications by treatment line, survival status at the data cut-off date, and date of death.

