21. SAP ADDENDUM 6.0

21.1 Post-L-MIND survival

Summary / analysis of OS

A Kaplan-Meier analysis for OS will be conducted focusing only on the period after the end of treatment of both MOR00208 and LEN. The following four patient subgroups will be defined:

Subgroup	Treatment status	PFS Event / Censoring status (based on INV)	Post-L-MIND anti-DLBCL medication
1	Both MOR00208 and LEN discontinued	PFS Event	Experienced (at least one further treatment)
2	Both MOR00208 and LEN discontinued	PFS Event	No post-L-MIND anti-DLBCL medication at all
3	Both MOR00208 and LEN discontinued	Censored for PFS follow-up	Experienced (at least one further treatment)
4	Both MOR00208 and LEN discontinued	Censored for PFS follow-up	No post-L-MIND anti-DLBCL medication at all

Baseline for the OS analysis is the earliest point in time when both requirements are met:

- a) Both study drugs discontinued
- b) PFS event / censoring happened

A Kaplan-Meier plot will also be generated displaying the four subgroups.

A Table showing the censorings reasons (ongoing at data cut-off, lost to follow-up, ICF withdrawal etc.) for each subgroup will be produced.

A Listing will be provided showing all post-L-MIND anti-DLBCL medications by treatment line, survival status at the data cut-off date, and date of death.

Swimmers plot

Based on the FAS, four swimmers plots will be generated for the four patient subgroups above. The following will be displayed:

- Bar length: [(Date of death or date censoring of OS follow-up) – (Date of end of treatment) + 1].

STATISTICAL ANALYSIS PLAN

 MorphoSys AG
 MOR208C203

- An arrow head at the end of the bar will indicate if OS follow-up is still ongoing at data cut-off, or the point in time when a patient was censored for OS follow-up. A blunt end will indicate that the patient has died.
- Symbols will be used to indicate the initiation every new treatment line after the treatment with MOR00208 + LEN.

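### Post-study overall survival is split by whether a later anti-DLBCL medication was ever given, with time zero normally before that therapy, so the curves carry guarantee-time bias in favour of recipients

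*SAP*

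**What the plan says.** SAP Section 20.4.1 (Addendum 5.0) states: "A Kaplan-Meier analysis for OS will be conducted focusing only on the period after the end of treatment of both MOR00208 and LEN". Four subgroups cross IRC-based PFS status (event or censored) with later treatment. Subgroups 1 and 3 had at least one later line. Subgroups 2 and 4 are labelled "No post-L-MIND anti-DLBCL medication at all".

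On the origin of the clock: "Baseline for the OS analysis is the earliest point in time when both requirements are met". The two requirements are that both drugs are discontinued and that the PFS event or censoring has happened, so time zero is the later of those two dates. On display: "A Kaplan-Meier plot will also be generated displaying the four subgroups". For the PFS-event rows, the table adds in brackets that deaths are left out.

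Section 21.1 (Addendum 6.0) repeats the split and the time zero with investigator-assessed PFS. Its PFS-event rows do not carry the bracketed exclusion of deaths.

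Neither section specifies a landmark, a time-dependent exposure or a caveat. Neither specifies a log-rank test or hazard ratio for these subgroups.

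**The concern.** The subgroups are defined by something that normally happens after the clock has started. To be counted as a recipient, a patient must survive from time zero to the start of the next therapy, and that stretch is credited to the recipient curve as time in which death was impossible. Every death in the same stretch goes to a 'none' curve. The two curves would separate even if later therapy had no effect on survival.

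What is at stake is how the plot is read. SAP Section 3 says planned analyses may go into study reports, regulatory submissions or manuscripts. The trial has no control arm against which a reader could separate this artefact from a real effect of later treatment. Section 21.1 repeats the split and the time zero, so it cannot reveal the problem.

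**Working it through.** **Step 1. Does time zero precede the next therapy?** Normally it does.

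- If non-study therapy starts before progression, SAP Table 13 censors PFS at the "Date of last adequate tumour assessment before start of non-study cancer treatment". The PFS part of time zero then falls before therapy.
- The note in SAP Section 20.9 says "PFS follow-up stops with treatment discontinuation (a post-treatment PFS follow-up is not conducted in L-MIND", so the PFS date does not normally fall after treatment ends.
- Exception: Protocol Section 6.7 and Table 5 footnote 21 allow other antineoplastic therapy while MOR00208 continues after progression. For such a patient, therapy can start before time zero.

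**Step 2. How large could the bias be?** The plan gives no figure to reproduce, so this is an illustration in which later therapy has no effect. All inputs are assumptions:

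- Death from time zero is exponential with median 4 or 6 months, rate λ = ln 2 / median. For context, Protocol Section 1.2 puts median survival below 6 months for non-responders to second-line therapy and below one year after relapse from it.
- The wait to next therapy is exponential with median 1.5 to 3 months, rate μ = ln 2 / median, independent of death.
- A share q of patients is headed for further therapy; the rest never receive it.

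Without censoring, the survival functions in the ever/never groups are:

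- Ever treated: S(t) = [(λ+μ)e^(−λt) − λe^(−(λ+μ)t)] / μ, which does not depend on q.
- Never treated: S(t) = [qπe^(−(λ+μ)t) + (1−q)e^(−λt)] / [qπ + 1 − q], where π = λ/(λ+μ) is the chance of dying before therapy.

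Worked case: median survival 6 months, median wait 2 months, q = 0.7.

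- λ = 0.1155, μ = 0.3466, π = 0.25.
- Ever treated at 6 months: (0.4621 × 0.5 − 0.1155 × 0.0625) / 0.3466 = 0.65.
- Never treated at 6 months: (0.7 × 0.25 × 0.0625 + 0.3 × 0.5) / (0.175 + 0.3) = 0.34.

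Setting S(t) = 0.5 gives medians in months:

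| Median OS / wait | Ever treated | Never, q = 1.0 | Never, q = 0.7 | Never, q = 0.5 |
|---|---|---|---|---|
| 4 / 1.5 | 5.7 | 1.1 | 2.3 | 3.0 |
| 6 / 1.5 | 7.9 | 1.2 | 3.5 | 4.6 |
| 6 / 2 | 8.4 | 1.5 | 3.4 | 4.5 |
| 6 / 3 | 9.2 | 2.0 | 3.6 | 4.5 |

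A separate null simulation used 18 scenarios: median survival 6 or 12 months, median wait 1, 2 or 3 months, q = 0.5, 0.7 or 0.9, and administrative censoring at 12–36 months. The ever/never hazard ratio ran from 0.32 to 0.84. With therapy as a time-dependent exposure the rate ratio was 1.00–1.01, and with a 2-month landmark 0.99–1.01.

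**Step 3. Does this hold for subgroups 3 and 4?** These patients are censored for PFS. Subgroup 4 can include people who stopped both drugs without progression and needed nothing further. Suppose they make up 30% of the PFS-censored patients, with median survival 36 months and no later therapy, and the rest follow the worked case. The never-treated curve is then

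{0.3e^(−λ′t) + 0.7[0.3e^(−λt) + 0.175e^(−(λ+μ)t)]} / {0.3 + 0.7 × 0.475}, with λ′ = ln 2 / 36.

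Its median is 9.9 months against 8.4 for recipients. The bias is still present, but the observed order is reversed.

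**Step 4. What does the missing exclusion in 21.1 do?** PFS includes death from any cause (SAP Section 10.2.2). If such a death counts as the PFS event in 21.1, time zero is the date of death. Under the SAP Section 6.9 formula (end minus start plus one), OS is 1 day. Table 13 censors PFS once non-study therapy has started before progression, so these patients have had no later therapy and fall in subgroup 2.

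**The case against.** The strongest reply is that this is late, supportive, descriptive output. No test or hazard ratio is planned here, whereas SAP Sections 10.12.3 and 11.4 specify hazard ratios, and 10.12.3 log-rank tests, for other subgroups. The SAP claims no benefit of later therapy. The swimmers plots mark each therapy start and a listing gives therapies and deaths, so a careful reader can see the timing. A time-dependent Cox model would add inference that the plan avoids, in about 80 patients split four ways. Much of this stands: it limits the consequence and argues for a plain display rather than a new hazard ratio. It does not remove the bias from the Kaplan-Meier curves, and four curves on one plot invite comparison.

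Two stronger readings are tempting. A reader might infer that the plot is bound to show a large gap in favour of recipients. Step 3 shows that this is not assured for subgroups 3 and 4. A reader might also take 1.1–2.0 months as the expected median without later therapy. That result needs every patient to be headed for further therapy, so that the 'none' group consists only of early deaths. At 70% it becomes 2.3–3.6 months and at 50% 3.0–4.6 months. The documents give no such share.

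**Conclusion.** The point holds for both sections. Guarantee-time bias in favour of recipients is built into the ever/never split, most clearly for subgroup 1 against 2. Section 21.1 is more exposed than 20.4.1 if deaths count as PFS events there.

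The size cannot be computed from the documents. Under the null assumptions in the working, median OS is about 5.7–9.2 months with and 1.1–4.6 months without later therapy. The model assumes exponential times and independence of the wait from prognosis.

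A reader might go on to infer that the trial's efficacy results are compromised. The documents do not support that: the primary ORR and the main OS analysis (SAP Section 10.4.4) do not use this split. The change is worth making because the outputs may be published and the correction is cheap.

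**What to change.** In both 20.4.1 and 21.1, replace the ever/never split by one of these:

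- A landmark fixed in advance, for example 60 days after the analysis baseline. Classify patients by whether later therapy had started before it, and draw the curves from the landmark among those still followed.
- A Simon-Makuch plot in which each patient moves from the untreated to the treated risk set on the date therapy starts.

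In 21.1, add the restriction from 20.4.1, so that a death that is itself the PFS event does not enter subgroup 2. State how patients whose other therapy began before time zero are classified.

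Beside the plot, say that the comparison is descriptive and that confounding by fitness for further therapy, or by lack of need for it, remains. Neither method removes that.

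No new data are needed: therapy start dates already feed SAP Sections 8.7.6 and 20.4.2, and the survival calls in Protocol Section 7.2.5 ask about later therapy. The cost of a landmark is losing patients who die or are censored before it, in subgroups that are already small.
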